9.4.3 ECG

For the treatment-emergent ECG measurements, a summary of observed values and change from baseline values will be provided by treatment group at each visit for the following ECG interval measurements (in msec): RR interval, PR interval, QT interval, and QTcF interval, QRS duration, and Heart Rate (beats per minute).

The number and percentage of subjects meeting at least 1 threshold analysis criterion during the TE period will be summarized by treatment group. The threshold analysis criteria are provided in [Appendix F](#).

9.4.4 Vital Signs

For the treatment-emergent vital signs measurements, the observed values and change from baseline values will be summarized by treatment group at each visit, as applicable. The following vital signs parameters will be summarized: systolic and diastolic blood pressure (mm Hg), body temperature (°C), pulse rate (beats per minute), and respiratory rate (breaths per minute).

The number and percentage of subjects meeting at least 1 threshold analysis criterion during the TE period will be summarized by treatment group. The threshold analysis criteria are provided in [Appendix F](#).

9.4.5 Pulse Oximetry

For the treatment-emergent pulse oximetry measurements, a summary of observed values and change from baseline values will be provided by treatment group at each visit, for the percent of oxygen saturation.

The number and percentage of subjects with shift changes from baseline (normal/missing and low according to the reference range) to the lowest percent of oxygen saturation during the TE period will be summarized by treatment group. The reference range for normal oxygen saturation is specified as >95%, and <=95% for low oxygen saturation.

9.4.6 Ophthalmologic Examinations

The ophthalmologic examination results will be conducted only for subjects who are <18 years of age on the date of informed consent and presented in individual subject data listings only.

9.4.7 Physical Examination

All PE findings will be presented as an individual subject data listing only.

9.4.8 COVID-19 Impacted Visits

A listing containing subjects' visits impacted due to COVID-19 will be provided.

9.4.9 Supportive Safety Analysis

9.4.9.1 Adverse Events of Special Interest

For this study, elevated transaminases events and rash events, as determined by MedDRA preferred terms in the respective Customized MedDRA Queries (CMQ), are considered as adverse events of special interest.

For treatment-emergent elevated transaminases events and rash events, the following categories will be summarized by treatment group:

- Subjects with events
- Subjects with events by maximum severity
- Subjects with events leading to treatment discontinuation
- Subjects with events leading to treatment interruption
- Subjects with serious events
- Subjects with related serious events
- Subjects with events leading to death
- Duration of events
- Time-to-onset of first event

In addition, for treatment-emergent rash events, these categories will be summarized for the following subgroups:

- Sex (male, female)
- Female subjects with concomitant hormonal therapy (Yes, No)

9.4.9.2 Hormonal Therapy

The number of subjects who used hormonal therapy concomitantly will be summarized by treatment group based on the Safety Set.

10 SUMMARY OF Interim and IDMC ANALYSIS

10.1 Interim analysis

No interim analysis is planned for this study.

10.2 IDMC Analysis

The IDMC's objectives and operational details are defined in a separate document (IDMC Charter) which was finalized before the first subject was screened in the study. The IDMC's planned safety reviews of study data are outlined in the IDMC Charter and IDMC SAP.

12 LIST OF APPENDICES

Appendix A: Analysis Visit Windows for Safety and Efficacy Assessments

Table 12-1 Analysis Visit Windows for Safety and Efficacy Assessments			
Assessment	Visit¹	Target Study Day	Analysis Visit Window (in study days)^{2,3,4}
Safety Assessment			
Serum Chemistry	Day 1 (Baseline)	1	≤1 Pre-dose
Hematology	Day 15	15	[1, 22]
Standard 12-lead ECG	Week 4	29	(22, 43]
Vital Signs (excluding BMI, Weight, Height and their Z-scores)	Week 8	57	(43, 85]
	Week 16	113	(85, 141]
	Week 24	169	(141, 183]
	Safety Follow-up	Not applicable	Use nominal visit
Coagulation	Day 1 (Baseline)	1	≤1 Pre-dose
	Week 24	169	[1, 183]
	Safety Follow-up	Not applicable	Use nominal visit
Efficacy Assessment			
Spirometry, Weight, Height and BMI (and the corresponding z-score) ⁵	Day 1 (Baseline)	1	≤1 Pre-dose
	Day 15	15	(1, 22]
	Week 4	29	(22, 43]
	Week 8	57	(43, 85]
	Week 16	113	(85, 141]
	Week 24	169	(141, 183]
	Safety Follow-up	Not applicable	>183
Sweat Chloride	Day 1 (Baseline)	1	≤1 Pre-dose
	Day 15	15	(1, 22]
	Week 4	29	(22, 43]
	Week 8	57	(43, 85]
	Week 16	113	(85, 141]
	Week 24	169	(141, 183]
CFQ-R ⁵	Day 1 (Baseline)	1	≤1
	Week 4	29	(1, 43]
	Week 8	57	(43, 85]
	Week 16	113	(85, 141]
	Week 24	169	(141, 183]
	Safety Follow-up	Not applicable	>183

Notes:

¹ Visit name for analysis purpose is used to report data in tables and figures.

² The analysis visit windows will be applied using the following rules for both scheduled and unscheduled visits:

- a. If no numerical measurement is available within a visit window, the measurement will be considered missing for the visit.
- b. If there is more than 1 numerical measurement available within a visit window, use the following rules:
 - i. The measurement closest to the target day will be used; or
 - ii. If there are multiple measurements with the same distance from the target day, the latest measurement will be used. If the latest measurement cannot be determined, then unscheduled visit will be selected.

Table 12-1 Analysis Visit Windows for Safety and Efficacy Assessments

Assessment	Visit ¹	Target Study Day	Analysis Visit Window (in study days) ^{2,3,4}
³ For measurements collected on the date of first dose of study drug, if it cannot be determined whether the measurement is before or after the first dose:			
a. Scheduled measurement will be treated as pre-dose observation. b. Unscheduled measurement will be treated as post-dose observation.			
⁴ For safety Assessment, Safety Follow-up analysis visit will be based on nominal Safety Follow-up visit. If a subject doesn't have a nominal Safety Follow-up visit but has an ETT visit with study day >183, then the ETT visit will be mapped into Safety Follow-up analysis visit.			
⁵ For efficacy analysis, if there are multiple assessments >183, then nominal Safety Follow-up visit will be mapped to Safety Follow-up visit. If there is only ETT assessment > 183, the ETT visit will be mapped to the Safety Follow-up visit;else if there are multiple assessments with >183 then select the earliest record.			
Derived Variables:			
1. Age (in years) at first dose date and nominal visit (for demographics, listing and the calculation of [percent] predicted spirometry variables):			
Obtain age at informed consent (in days) in yy mm format (e.g., 24 years, 6 months) from screening vital signs page, and add 0.5 month to convert to days.			
Obtain informed consent date .			
Then age (in years) at first dose or nominal visit = [(first dose date or nominal visit date – informed consent date) in days + age at informed consent (in days)]/365.25.			
2. Age (in months) at nominal visit (for use in calculation of BMI and weight z-score):			
Obtain age at informed consent (in months) in yy mm format (e.g., 24 years, 6 months) from screening vital signs page.			
Obtain informed consent date .			
Then age (in months) at nominal visit = integer part of {[(age at informed consent (in months) + 0.5 + diff(nominal visit date, informed consent date) in months)] + 0.5}.			
3. Missing first dose date or last dose date			
If the first dose date is missing, use Day 1 visit date to impute.			
If the last dose date is missing or partial date is reported, the last dose date will be imputed based on, in descending order priority, the ETT visit date, last visit date before the Safety Follow-up, or the last study drug administration date from EX SDTM domain, as appropriate. The imputation algorithm will ensure the imputed last dose date does not exceed the study participation end date.			
4. Sweat Chloride:			
Non-missing sweat chloride concentrations from the left arm and right arm with assessment end date/time for a given arm up to 30 minutes after first dose time in treatment period will be considered for baseline.			
5. Electrocardiogram:			
Baseline is defined as the most recent pretreatment measurement before the first dose of study drug in the Treatment Period. If multiple ECG measurements are obtained on the same calendar day during the TE period,			
○ For summary purpose, the calculated average ECG will be used as the ECG value on that day;			
○ For threshold analysis purpose, all reported ECG values will be used.			

Appendix B: Imputation Rules for Missing Prior/Concomitant Medication Dates

Imputation rules for missing or partial medication start/stop dates are defined below:

1. Missing or partial medication start date:
 - a. If only DAY is missing, use the first day of the month.
 - b. If DAY and Month are both missing, use the first day of the year.
 - c. If DAY, Month and Year are all missing, use a date before the first dose date (in practice, use the informed consent date to impute).
2. Missing or partial medication stop date:
 - a. If only DAY is missing, use the last day of the month.
 - b. If DAY and Month are both missing, use the last day of the year.
 - c. If DAY, Month and year are all missing, assign ‘continuing’ status to stop date (in practice, use the End of Study Date to impute).

In summary, the prior, concomitant, or post categorization of a medication is described below.

Table 12-2 Logic for determining the Category of a Medication

Medication Start Date	Medication Stop Date		
	< First Dose Date of Study Drug	\geq First Dose Date and \leq End Date of TE Period	> End Date of TE Period
< First dose date of study drug	P	PC	PCA
\geq First dose date and \leq End date of TE period	-	C	CA
> End date of TE period	-	-	A

P: Prior; C: Concomitant; A: Post

Imputation rules for missing and/or partial dates of non-pharmacological treatment/procedure will follow the same imputation rule.

Appendix C: Details of GLI Equations for Calculating ppFEV₁

Percent predicted values will be calculated for parameters of FEV₁, FVC, FEV₁/FVC, and FEF_{25%-75%} using the Quanjer GLI-2012 Regression Equations and Lookup Tables.

The regression equations and lookup tables required to implement the Quanjer GLI-2012 predicted values are available in:

Philip H. Quanjer, Sanja Stanojevic, Tim J. Cole, Janet Stocks. Quanjer GLI-2012 Regression Equation and Lookup Tables (Version 7 April 2013). Global Lung Function Initiative. [online] Available at: <http://www.ers-education.org/home/browse-all-content.aspx?idParent=138978> [Accessed Jul. 9, 2019].

The instructions and tools on how to implement the Quanjer GLI-2012 equations are:

Philip H. Quanjer, Sanja Stanojevic, Tim J. Cole, Janet Stocks. Implementing GLI-2012 regression equations (Version 19 July 2015). Global Lung Function Initiative. [online] Available at: <http://www.ers-education.org/home/browse-all-content.aspx?idParent=138979> [Accessed Jul. 9, 2019].

Sanja Stanojevic. GLI-2012 - SAS Macro (Version 2, 7 April 2013). Global Lung Function Initiative. [online] Available at: <http://www.ers-education.org/home/browse-all-content.aspx?idParent=138988> [Accessed Jul. 9, 2019].

Data handling rule for spirometry is as follows:

- Input age with at least 2 decimal place
- Use height at screening regardless if height is collected at other study visits for subjects whose age at informed consent is >21 years. For subjects with age <=21 years, height collected at the respective visit should be used.
- For race, map CRF black or AA to black, all other races in CRF (except white) are mapped to 'other'; multiple checks for race in CRF are also mapped to 'other'; white is a reference race in the equations and assumes 0 values for all race coefficients in the GLI equations.

Appendix D: Steps for Multiple Imputation

For the multiple imputation (MI) to be applied to the MMRM for the sensitivity analysis of the primary efficacy endpoint, the following steps will be followed:

Imputation distribution

The imputation distribution for the missing absolute change from baseline in ppFEV₁ at visit t will be a normal distribution. All subjects in the corresponding analysis set (e.g., FAS) will be classified into one of three categories based on the following rules:

- Non-missing category: Subjects who have a ppFEV₁ assessment at the last timepoint of the dependent variable. Given the primary analysis method, this corresponds to the subjects who have a non-missing absolute change from baseline in ppFEV₁ at Week 24.
- Missing category 1: Subjects with missing absolute change from baseline in ppFEV₁ at the last timepoint of the dependent variable (Week 24), who discontinued treatment because of AEs, noncompliance with study drug, death, or physician decision, or because the subject refused further dosing or required prohibited medication.
- Missing category 2: Subjects with missing absolute change from baseline in ppFEV₁ at the last timepoint of the dependent variable (Week 24), who completed the protocol-specified treatment or discontinued treatment for any reason not listed in Category 1.

Imputation algorithm

We will use the following algorithm that relates the mean of the missing absolute change from baseline in ppFEV₁ at visit t to the missing categories defined above. The algorithm will be implemented within each treatment group as follows:

- Missing category 1: randomly draw a sample from the normal distribution (μ_{25}, σ^2) , where μ_{25} is the 25th percentile of the non-missing absolute changes from baseline in ppFEV₁ at visit t and σ^2 the sample variance estimated using the non-missing absolute changes at visit t .
- Missing category 2: randomly draw a sample from the normal distribution (μ, σ^2) , where μ is the mean of the non-missing absolute changes from baseline in ppFEV₁ at visit t and σ^2 is the sample variance estimated using the non-missing absolute changes at visit t .

Analysis model

The complete MI method is described below:

- Form an “imputed dataset” by imputing missing values at each visit for those subjects who have a missing value at the visit and have all subsequent values missing. The appropriate normal distribution specified in the algorithm above will be used for each such subject, based on their category.
- Repeat this process K ($K=20$) times to form K imputed datasets.
- Fit the same MMRM model as the one used for primary analysis to each imputed dataset to estimate the absolute change at Week 4.
- Combine the results from the analyses of K imputed datasets using the SAS procedure MIANALYZE to derive the MI estimator.

Let θ be the true treatment difference. Denote by $\tilde{\theta}_k$ the estimate of θ from the k^{th} imputed dataset, and the corresponding estimate of the variance is denoted by V_k . The MI estimator of θ , $\tilde{\theta}_{\text{MI}}$, is the average of the K individual estimates.

The estimated variance of $\tilde{\theta}_{\text{MI}}$ is a combination of the between- and within-imputation variability as follows: $V_{\text{MI}} = W + \left(1 + \frac{1}{K}\right)B$, where $W = \frac{1}{K} \sum_{k=1}^K V_k$ is the within-imputation variability and is $B = \frac{1}{K-1} \sum_{k=1}^K (\tilde{\theta}_k - \tilde{\theta}_{\text{MI}})^2$ is the between-imputation variance. The statistic $T = \frac{\tilde{\theta}_{\text{MI}} - \theta}{\sqrt{V_{\text{MI}}}}$ has an approximate t_V distribution⁷, where $V = (K-1)(1 + \frac{W}{B})^2$.

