9.3.1.2 Primary Analysis

The primary analysis will be performed using a MMRM with change from baseline at Day 15, Week 4, Week 8, Week 16, and Week 24 as the dependent variable. The model will include treatment group, visit, and treatment by visit interaction as fixed effects, with continuous baseline ppFEV₁, age at screening (<18 versus \geq 18 years of age) and mutation group (contains \geq 1 RF-like mutation versus does not contain an RF-like mutation) as covariates. The model will be estimated using restricted maximum likelihood. Denominator degrees of freedom for the *F*-test for fixed effects will be estimated using the Kenward-Roger approximation². An unstructured covariance structure will be used to model the within-subject errors. If the model estimation does not converge, a compound symmetry covariance structure will be used instead. Conditional on the observed data and covariates, missing data will be assumed to be missing at random.

The primary result obtained from the model will be the estimated treatment difference through Week 24, defined as the averaged treatment effects estimated at Week 4, Week 8, Week 16, and Week 24. The adjusted means with 2-sided 95% CIs and 2-sided *P* value will be provided. Furthermore, the treatment difference at each post-baseline visit obtained from the model will also be provided.

The estimated within group change from baseline and treatment difference at each post-baseline visit, obtained from the model, will be provided. The estimated within group change and its SE at each post-baseline visit will also be plotted by treatment group. In addition, the post-baseline raw values and the absolute change from baseline at each post-baseline visit will be summarized descriptively (n, mean, SD, median, minimum, and maximum).

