9.3.1.3 Supportive Analyses

There will be no supportive analysis for the primary efficacy endpoint.

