9.3.1.4 Sensitivity Analyses

MMRM based on Multiple Imputation (MI)

An underlying assumption of the MMRM method is that data are missing at random. To minimize the amount of missing data, subjects who prematurely discontinue study drug treatment will continue to complete all scheduled study visits for spirometry and other efficacy assessments.

To assess the impact of missing data and the assumption that data are missing at random, a multiple imputation algorithm will be used if at least 10% of the subjects have missing changes

in ppFEV₁ at Week 24 in any treatment group. Missing absolute change from baseline in ppFEV₁ assessments will be imputed starting from the first visit with missing values, for which all subsequent visits through Week 24 are also missing. For intermediate missing data, i.e., missing values that fall between two non-missing ones, it is reasonable to assume that they are missing at random and therefore will not be imputed. An MMRM analogous to that for the primary analysis of the primary endpoint will be applied to each imputed dataset and the relevant MI estimators will be reported. Details for the MI steps are presented in [Appendix D](#).

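### The only check of the missing-at-random assumption ignores dropouts' own earlier visits, can move either way relative to the MMRM, and is skipped when under 10% are missing in both arms

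*SAP*

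**What the plan says.** SAP 9.3.1.2 fits an MMRM to the changes at Day 15 and Weeks 4, 8, 16 and 24, and states: "Conditional on the observed data and covariates, missing data will be assumed to be missing at random". The treatment difference through Week 24 is "defined as the averaged treatment effects estimated at Week 4, Week 8, Week 16, and Week 24".

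SAP 9.3.1.3 reads: "There will be no supportive analysis for the primary efficacy endpoint". SAP 9.3.1.4 then gives one sensitivity analysis, a multiple imputation (MI), whose purpose is "To assess the impact of missing data and the assumption that data are missing at random". It runs only if at least 10% of subjects in any treatment group lack a Week 24 change. The protocol (12.3.3.1 and 12.3.3.5) leaves missing-data sensitivity analyses to the SAP, so nothing else is planned.

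SAP Appendix D imputes only values missing from some visit onward through Week 24. On the reference arm it says: "The algorithm will be implemented within each treatment group as follows". Each draw is normal, with the variance of the observed changes at that visit.

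- **Category 1** (adverse event, noncompliance, death, physician decision, refusal of further dosing, prohibited medication): the centre "is the 25th percentile of the non-missing absolute changes from baseline in" ppFEV₁ at that visit.
- **Category 2** (treatment completed, or any other reason for stopping): the centre "is the mean of the non-missing absolute changes from baseline in" ppFEV₁ at that visit.

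The analysis step is: "Fit the same MMRM model as the one used for primary analysis to each imputed dataset to estimate the absolute change at Week 4".

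**The concern.** A check of the missing-at-random (MAR) assumption should replace it with something less favourable or more general. Category 2 does the opposite. The MMRM predicts a dropout's later values from that subject's earlier ones; Appendix D discards those values when it draws, although the observed ones stay in the MMRM fitted to each imputed dataset. That is in effect a missing-completely-at-random assumption, stronger than the one under test. A subject who was declining is imputed as an average member of the same arm.

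Category 1 is a real penalty, but it falls on placebo dropouts too. It can cancel, or favour drug, depending on which arm loses more.

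At stake is what a reader may conclude from agreement between the two analyses. If dropout depends on values nobody saw and is heavier on active, the MMRM is biased toward drug and this check may not show it. With missingness just under 10% in both arms there would be no check at all. The Week 4 target also means that, as written, the check does not estimate the primary quantity.

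**Working it through.** **Inputs from the documents** (SAP 7.2, 9.3.1.4, Appendix D): 180 active, 90 placebo; SD 9; 10% dropout; planned difference 4.0; two-sided alpha 0.05; trigger 10% in any arm; K = 20 imputations.

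**Assumptions not in the documents:** visit correlation, dropout mechanism, split of dropout by arm, share in category 1.

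**1. The plan's own figure.** With 162 and 81 completers, SE = 9 × √(1/162 + 1/81) = 1.22. Two-sample t power at 4.0 is 90.2%, which agrees with the stated 90% or so.

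**2. One dropout.** The 25th percentile of a normal with SD 9 lies 0.6745 × 9 = 6.07 points below the mean. Take a subject 9 points below the arm's remaining subjects at the previous visit, with correlation 0.7 and one earlier visit. MAR predicts 0.7 × 9 = 6.3 points below their mean.
- Category 2 imputes 0 below, which is 6.3 points above the MAR prediction.
- Category 1 imputes 6.07 below, about the same as MAR. It is a penalty relative to MAR only for subjects less than 6.07/0.7 = 8.7 points below.

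**3. The penalty between arms.** If all dropouts are category 1, the Week 24 difference moves, relative to mean imputation, by -(active share - placebo share) × 6.07:
- 15% vs 5%: -0.10 × 6.07 = -0.61
- 10% vs 10%: 0.00
- 5% vs 15%: +0.61, toward drug

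**4. Simulation against the MMRM.** Five visits, correlation 0.7 (compound symmetry), true difference 0. The dropout hazard after each of visits 1 to 4 is logistic(a - b·x/SD), where x is the latest observed value, b = 2, and a is tuned to the target missingness. There were 2,000 runs; Monte Carlo SE is at most 0.007. The result is MI minus MMRM, averaged over Weeks 4 to 24; plus favours drug.

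| Missing, active vs placebo | Half category 1 | All category 1 |
|---|---|---|
| 15% vs 5% | +0.44 | +0.24 |
| 12% vs 8% | +0.18 | +0.09 |
| 10% vs 10% | 0.0 | 0.0 |
| 5% vs 15% | -0.43 | -0.24 |

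Variations at 15% vs 5%:
- 20% in category 1: +0.56
- b = 1: +0.20 (half) and +0.01 (all)
- AR(1) correlation: +0.27 and +0.08
- category 1 linked to a poor last value (62% in category 1): +0.41
- dropout unrelated to value, all category 1: the sign reverses, -0.38 at 15% vs 5% and +0.39 at 5% vs 15%

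A second simulation used a true difference of 4.0, correlation 0.4 or 0.8, and dropout after Day 15 or Week 8 (100 runs, 4 imputations). MI minus MMRM ran from -1.16 to +1.18; the extremes had every dropout a poor responder in category 2. The MMRM stayed within about 0.04 of the full-data estimate, so the shift comes from the imputation. Equal dropout does not guarantee zero: at 10% vs 10% with poor-responder dropouts in category 2 on active and category 1 on placebo, the shift was +0.30 to +0.59.

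**5. Dropout driven by the unseen next value, 15% vs 5%.**

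| Slope b | MMRM bias toward drug | Further move, half category 1 | Further move, all category 1 |
|---|---|---|---|
| 2 | +0.29 | +0.26 | +0.07 |
| 1 | +0.16 | +0.11 | -0.08 |

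**6. Does the check run?** P = 1 - (1 - P[Bin(180, pA) ≥ 18]) × (1 - P[Bin(90, pP) ≥ 9]).

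| True missingness, active vs placebo | P(check runs) |
|---|---|
| 5% vs 5% | 4% |
| 8% vs 8% | 43% |
| 10% vs 10% | 79% |
| 9% vs 5% | 38% |
| 12% vs 8% | 88% |
| 15% vs 5% | 98% |

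Up to 17 of 180 plus 8 of 90, that is 25 of 270 (9.3%), could be missing with no check.

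**The case against.** The strongest case against concerns importance rather than the reading of the SAP.

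- **The drug-favouring pattern is assumed.** The plan has 10% dropout with no imbalance, where the shift is about zero if the category mix is also equal. Protocol 5.1 reports few discontinuations in earlier studies, and protocol 9.1.4 keeps subjects in scheduled visits after stopping drug. If the drug works as planned and both arms share one dropout rule driven by low values, placebo loses more: with 10% overall, b = 2 and a true difference of 4.0, 7.5% active vs 14.1% placebo. Appendix D then moves against drug, by -0.29 (half category 1) or -0.16 (all). This stands. It shows that the direction depends on the dropout pattern; it does not make the check a reliable stress test.
- **The size is modest.** +0.44 is 0.36 of the planning SE (0.44/1.22) and +0.18 is 0.15. This stands.
- **Category 1 covers the most informative reasons for stopping**, and a higher share shrinks the shift. True for value-driven dropout; with value-independent dropout and heavier placebo loss, a higher share pushes toward drug.
- **A sensitivity analysis need not always be less favourable.** Agreed. But one meant to probe MAR should not rest, for category 2, on a stricter assumption than MAR.
- **The trigger mostly skips when little is missing.** Largely true, since one arm suffices to fire it. It can still skip close to the planned rate, and running it always costs almost nothing.

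**Conclusion.** The point holds. The only planned check of MAR draws around own-arm centres without the subject's history, so its direction relative to the MMRM is set by which arm loses more subjects, why, and how they are categorised. In the main scenarios the shift is at most about 0.4 to 0.6 points, up to 14% of the planned 4.0 (0.56/4.0); +0.44 is 11% and +0.18 about 4%. More extreme assumptions reach about 1.2 points either way. With heavier active dropout driven by unseen values, the check mostly moves with the MMRM's bias or barely moves, so agreement between the two would be weak reassurance.

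These sizes rest on the assumed correlation, dropout slope, arm imbalance and category shares; the documents predict no imbalance. The primary test and the testing hierarchy are unaffected. This is an improvement worth making before data lock, not an error in the primary analysis.

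**What to change.** 1. In SAP 9.3.1.4, delete the 10% condition so that the analysis always runs.
2. In Appendix D, impute monotone missing changes within arm, visit by visit, by regression on baseline ppFEV₁, age group, mutation group and all of the subject's earlier changes, with parameters drawn (PROC MI, MONOTONE REG). Intermittent gaps can be filled by MCMC only to obtain a monotone pattern, then set back to missing before the MMRM, which keeps the present rule.
3. Add a tipping point: subtract d from every imputed value of all active-arm dropouts, categories 1 and 2, and nothing from placebo. Raise d in 1-point steps until the two-sided P value reaches 0.05. Do not rely on a decrement in both arms.
4. Report category 1 and category 2 counts by arm. SAP 9.2.1 already tabulates discontinuation reasons, but not these categories among subjects with missing Week 24 data.
5. In the analysis step of Appendix D, replace the Week 4 target by the through-Week-24 average of 9.3.1.2.

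**Check of the fix** (600 runs, covariates omitted; 300 for the tipping point):
- With d = 0 the regression MI differs from the MMRM by 0.00 at 15% vs 5%, 10% vs 10% and 5% vs 15%.
- With d = 3, for illustration only, it gives -0.31, -0.20 and -0.10, never toward drug. A 6.07-point decrement in both arms gives +0.42 at 5% vs 15%.
- With unseen-value dropout (15% vs 5%, b = 2), distance from the complete-data result is +0.29 for the MMRM, +0.57 for Appendix D and 0.00 for d = 3 on all active dropouts. Restricting d = 3 to category 1 leaves +0.15 (half category 1) or +0.24 (20%). The 0.00 belongs to this one d and scenario.
- At a true difference of 4.0 the median tipping d is 22 points (10% vs 10%, MAR) or 19 (15% vs 5%, unseen-value), so the table would also show when the result is robust.

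**Cost:** about half a page of Appendix D rewritten, one clause deleted, standard SAS code and one extra table, all before data lock.

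### The multiple-imputation sensitivity analysis is told to estimate the Week 4 change, not the through-Week-24 treatment difference it is meant to test

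*SAP*

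**What the plan says.** SAP 9.3.1.2 fits the model to five visits (Day 15 and Weeks 4, 8, 16 and 24). It takes as the primary result the treatment difference through Week 24, "defined as the averaged treatment effects estimated at Week 4, Week 8, Week 16, and Week 24". Secondarily, "the treatment difference at each post-baseline visit obtained from the model will also be provided".

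SAP 9.3.1.4 adds one sensitivity analysis, by multiple imputation, to examine the missing-at-random assumption. It is conditional: it "will be used if at least 10% of the subjects have missing changes" in ppFEV₁ at Week 24 in any treatment group. On the model it says: "An MMRM analogous to that for the primary analysis of the primary endpoint will be applied to each imputed dataset". The steps are left to Appendix D. SAP 9.3.1.3 states that no supportive analysis of the primary endpoint is planned.

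Appendix D sorts subjects by whether the change is missing "at the last timepoint of the dependent variable (Week 24"). Within each arm, category 1 (for example, discontinuation for adverse events) is drawn around the 25th percentile of the observed changes at the visit, and category 2 around their mean. Values are imputed at a visit for subjects "who have a missing value at the visit and have all subsequent values missing". The model is then fitted "to each imputed dataset to estimate the absolute change at Week 4". The combining rules that follow let θ "be the true treatment difference", with no time point.

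**The concern.** The extraction step names a different quantity from the one under test, in two respects. It points to a single early visit instead of the four-visit average, and it speaks of an absolute change instead of a between-group difference. No other part of the SAP makes Week 4 alone a target.

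The choice of visit matters because of the imputation rule. Anyone who leaves after giving a Week 4 value has nothing imputed at Week 4, so the unfavourable draws for that person fall on visits the Week 4 estimate does not use. The analysis exists to show whether the headline estimate survives a less favourable assumption about dropouts. Read literally, it would leave most later dropout out of the test and could look reassuring for that reason alone. Its result could be set only against the Week 4 difference, not against the primary result.

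The error would not announce itself: the primary model also yields a Week 4 treatment difference, so a program written this way would run and return a plausible number.

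**Working it through.** **The plan's own figure.** The sample-size statement (SAP 7.2: 180 v 90, SD 9, 10% dropout, 4.0 points, 2-sided 0.05) reproduces. With 162 v 81 completers, power is 90.4% by the normal approximation and 90.2% by the noncentral t, against about 90% stated. The point here does not alter it.

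**Which subjects have a Week 4 value imputed.** SAP Appendix A gives these spirometry windows in study days: Week 4 (22, 43], Week 8 (43, 85], Week 16 (85, 141], Week 24 (141, 183]. A Week 4 value is imputed only if all four are empty, meaning no spirometry from Day 23 through Day 183.

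**Inputs for the size of the effect**
- SD 9 points (SAP 7.2), applied here at each visit. The SAP would use the visit-specific observed values.
- 10% missing at Week 24. This is the planning dropout rate and also the run condition.
- Assumed: changes are normal, so the 25th percentile lies 0.6745 SD below the mean. The category 1 penalty relative to category 2 is 0.6745 × 9 = 6.07 points.
- Assumed: all missing subjects in one arm are category 1, and the other arm has no penalty.
- Assumed: the timing of dropout, which the documents do not give.

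**Formulas**
- Shift at Week 4 = 6.07 × fraction missing at Week 4.
- Shift in the primary average = 6.07 × mean fraction missing over Weeks 4, 8, 16 and 24.

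| Dropout timing | % missing at Weeks 4 / 8 / 16 / 24 | Mean % | Shift at Week 4 | Shift in average | Ratio |
|---|---|---|---|---|---|
| All between Weeks 16 and 24 | 0 / 0 / 0 / 10 | 2.5 | 0 | 0.15 | 0 |
| All between Weeks 8 and 16 | 0 / 0 / 10 / 10 | 5.0 | 0 | 0.30 | 0 |
| All between Weeks 4 and 8 | 0 / 10 / 10 / 10 | 7.5 | 0 | 0.46 | 0 |
| Even over 24 weeks | 1.67 / 3.33 / 6.67 / 10 | 5.42 | 0.10 | 0.33 | 0.31 |
| Front-loaded (square root of time) | 4.08 / 5.77 / 8.16 / 10 | 7.0 | 0.25 | 0.43 | 0.58 |
| All before Week 4 | 10 / 10 / 10 / 10 | 10 | 0.61 | 0.61 | 1.0 |

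For example, even accrual gives 6.07 × 0.0167 = 0.10 at Week 4 and 6.07 × 0.0542 = 0.33 for the average.

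**Less extreme imbalance.** If the other arm has half the category 1 share, the even-accrual shifts halve to 0.05 and 0.16. With equal shares and equal spread, both are about 0.

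**Check by simulation.** The table ignores indirect effects through the covariance matrix and shared covariates, so the comparison was simulated: 180 v 90 subjects, five visits, unstructured covariance, three covariates, within-subject correlation 0.5 and 0.8, 300 runs per scenario. The 10% dropout in the active arm was imputed once as category 1 and once as category 2. Mean change in the treatment difference (Week 4 / average):
- dropout spread uniformly after Week 4: 0.00 / −0.27, with the largest Week 4 change in any run 0.04
- even accrual: −0.10 / −0.33
- square-root accrual: −0.25 / −0.43
- all before Week 4: −0.60 / −0.60

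**The case against.** The strongest reply is that the SAP largely corrects itself. Appendix D introduces itself as serving the primary endpoint, 9.3.1.4 calls for a model like the primary one, Week 24 governs the trigger and the categories, and θ is a treatment difference. An absolute change cannot be pooled as a treatment difference, so any analyst must interpret the step, and the surrounding text shows how. The appendix has another slip nearby: its t-distribution cites reference 7, which is the growth charts, while the multiple-imputation paper is reference 6. That Week 4 is unintended is very likely. But 9.3.1.4 defers to Appendix D, and θ has no time point to override the one sentence that does name a visit. A prespecified analysis should not depend on the programmer's inference.

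The second reply concerns consequence. The analysis may never run: subjects who stop treatment stay in scheduled visits, and planned dropout sits exactly at the 10% trigger. When it does run, the shifts are modest. The standard error with 162 v 81 completers is 9 × √(1/162 + 1/81) = 1.22 points, so 0.33 is about 0.27 of it and 0.61 about half. Nothing here shows a changed conclusion at a 4.0-point difference. All of that stands.

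The third reply concerns the figures. They assume a one-sided penalty, and they compare category 1 with category 2 imputation, not with the primary model, which conditions on each subject's earlier values. They therefore do not measure the distance from the headline estimate. That is right, and the figures should be read only as showing how much of the penalty each target can register. If the SD of 9 describes a four-visit average, the visit-level SD is 9/√((1 + 3ρ)/4): 11.4 at ρ = 0.5 (penalty 7.7) and 9.8 at ρ = 0.8 (penalty 6.6). The absolute shifts would then be larger and the ratios unchanged.

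**Conclusion.** The concern holds. The current SAP text names the wrong quantity in its only planned sensitivity analysis of the primary endpoint, and it should be corrected. Under the stated assumptions, a Week 4 estimate registers none of the category 1 penalty when all dropout follows Week 4, about 31% of what the four-visit average registers when dropout is even, 58% when it is front-loaded, and all of it only when every dropout precedes Week 4. In the one-arm case the averaged shift that should be visible is 0.15 to 0.61 points, or 4% to 15% of the 4.0-point design difference. With balanced category 1 shares it is close to zero. These sizes depend on dropout timing and arm imbalance, which the documents do not give; the textual contradiction does not. The primary analysis, its P value, the testing hierarchy and the power are untouched.

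**What to change.** Replace the extraction step in Appendix D with wording such as: *Fit the primary-analysis MMRM to each imputed dataset and estimate the between-group difference in ppFEV₁ change through Week 24, as the mean of the treatment effects at Weeks 4, 8, 16 and 24.* Define θ in the next paragraph as that same difference.

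The cost is one line plus the matching definition, with no new data and no added analysis. SAP Section 4 provides the route: a documented amendment before data lock. The documents do not show whether lock has passed. If it has, run the analysis on the through-Week-24 difference and report the departure from Appendix D in the clinical study report, as Section 4 already requires.
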